#### **6.5.6.7. Pregnancy Reporting**

If a female patient becomes pregnant during the study through study completion, the Investigator must report the pregnancy to the Sponsor or designee within 24 hours of being notified of the pregnancy. Details of the pregnancy will be recorded on the pregnancy reporting form. The patient should receive any necessary counseling regarding the risks of continuing the pregnancy, the possible effects on the fetus, and be counseled to not breastfeed for 90 days after the last dose of study drug.

The pregnancy should be followed by the Investigator until completion. At the completion of the pregnancy, the Investigator will document the outcome of the pregnancy. If the outcome of the pregnancy results in a postpartum complication, spontaneous abortion, stillbirth, neonatal death, or congenital anomaly, then the Investigator should follow the procedures for reporting an SAE as outlined in Section 6.5.6.4.

#### **6.5.6.8. Overdose Reporting**

An overdose is defined as any dose administered to or taken by a patient (accidentally or intentionally) that exceeds the highest daily dose, or is at a higher frequency, than included in the protocol for the patient's weight category. The Investigator will decide whether a dose is to be considered an overdose, in consultation with the Sponsor. In the event of an overdose, the actual dose administered must be recorded in the eCRF.

All reports of overdose (with or without an AE) must be reported within 24 hours to the Sponsor or designee.

#### **6.5.7. COVID-19 Data Collection**

Information on the COVID-19 infection status of the patient, if known, and other information on the impact of the COVID-19 pandemic on the patient's participation in the study will be collected.

### **6.6. Biomarkers, DNA Genotyping, and Biospecimen Repository**

Alnylam's RNAi therapeutics platform permits the highly specific targeting of investigational therapies based on genetic sequence. It is possible that variations in the target genetic sequence will result in variations in drug effect. More generally, genetic variations may account for the well-described heterogeneous manifestations of disease in patients with PH1, as well as their responses to treatment.

Where allowed per local regulations, ethics committee (IRB/IEC) approval, and legal guardian consent (and patient assent, where applicable), samples will be collected as part of this study to permit exploratory investigations and the application of novel approaches to bioanalyses that may further elucidate the outcomes of this study, or potentially advance understanding of the safety, mechanism of action, and/or efficacy of lumasiran.

Biological specimens will be collected at the intervals indicated in the Schedules of Assessment (see [Table 1](#), [Table 2](#), [Table 3](#), and [Table 4](#)). Potential exploratory investigations may include DNA, RNA, or biochemical metabolite assessments as they relate to disease progression, efficacy or safety.

The biospecimen repository will also include residual material from routine samples (safety laboratory samples, PK samples, etc.) that are obtained during the study.

These specimens will be securely stored in a central biorepository for up to 10 years following the completion of this clinical study (ie, last patient last visit), or as per local regulations. After 10 years have elapsed, samples will be destroyed.

Details regarding the collection, processing, storage, and shipping of the samples will be provided in the Laboratory Manual.

Exploratory analysis of these biospecimens will be performed by Alnylam Pharmaceuticals or its designees.

When biobanking is permitted by local regulation, study participants will be advised during the informed consent process of these biobanking details and the potential for exploratory investigation of their samples.

## 6.7. Developmental Assessments

The Vineland Adaptive Behavior Scale will be assessed at the timepoints specified in the Schedules of Assessment (see [Table 1](#), [Table 2](#), [Table 3](#), and [Table 4](#)), and may be completed up to 4 months after the intended time point during periods of time when the COVID-19 pandemic impedes the ability of patients to travel to the study site, to assess the achievement of developmental milestones over time. This tool assesses the domains of communication, daily living skills, socialization, and motor skills. The survey can be completed in 20-60 minutes.

## 6.8. Patient/Caregiver Experience and Impact Questionnaire

The patient/caregiver experience and impact questionnaire will be used to assess the experiences of patients living with PH1 and their caregivers, including the impact of the disease on their lives with respect to their need to relocate/travel for treatment, and the number and type of healthcare providers they use. The questionnaire will also assess the impact on patients' education and caregivers' employment and education, as applicable. This questionnaire will be completed by the caregiver (reporting on behalf of the patient for patient experience items) at the time points specified in the Schedules of Assessment (see [Table 1](#), [Table 2](#), [Table 3](#), and [Table 4](#)) when feasible, and may be completed up to 4 months after the intended time point during periods of time when the COVID-19 pandemic impedes the ability of patients to travel to the study site.

# 7. STATISTICS

A Statistical Analysis Plan (SAP) will be finalized before database lock. The plan will detail the implementation of the statistical analyses in accordance with the principle features stated in the protocol. For information on study endpoints, see [Section 2](#).

## 7.1. Determination of Sample Size

The planned enrollment for the study is 20 patients. The sample size was determined based on feasibility considerations, not power calculations.

## 7.2. Statistical Methodology

Statistical analyses will be primarily descriptive in nature.

For categorical variables, summary tabulations of the number and percentage of patients within each category (with a category for missing data) will be presented. For continuous variables, descriptive statistics will be presented (ie, number of patients, mean, median, standard deviation, standard error, minimum and maximum values).

All data will be provided in by-patient listings. Additional data summaries to help understand any impact of COVID-19 on efficacy and safety assessments will be outlined in the SAP.

### 7.2.1. Populations to be Analyzed

The populations (analysis sets) are defined as follows:

- Safety Analysis Set: All patients who received any amount of study drug will be grouped according to the treatment actually received.

- Efficacy Analysis Set: All patients who received any amount of lumasiran and have at least one valid spot urinary oxalate:creatinine ratio value at baseline and at least one valid spot urinary oxalate:creatinine ratio value from assessment(s) at Month 3 to Month 6.
- PK Analysis Set: All patients who received any amount of study drug and have at least 1 postdose blood sample for PK parameters and have evaluable PK data.

The Safety Analysis Set will be used for safety analyses and sensitivity analysis of efficacy. The Efficacy Analysis Set will be used to evaluate efficacy endpoints. The PK Analysis Sets will be used to conduct PK analyses.

#### **7.2.2. Examination of Subgroups**

Subgroup analyses may be conducted for selected endpoints. Detailed methodology will be provided in the SAP.

#### **7.2.3. Handling of Missing Data**

Handling of missing data will be described in the SAP.

#### **7.2.4. Baseline Evaluations**

Demographics and other disease-specific baseline characteristics will be summarized for the Safety Analysis Set.

#### **7.2.5. Efficacy Analyses**

The analysis of the efficacy endpoints will be based upon the Efficacy Analysis Population. Descriptive summaries will be provided for the primary endpoint percent change in urinary oxalate excretion from baseline to Month 6. The analysis will be performed using a mixed-effect model for repeated measures (MMRM) approach. The outcome variable is percent change from baseline in spot urine oxalate:creatinine ratio. The model includes baseline value as covariate and fixed effect terms including treatment arm and visit (Months 3, 4, 5, 6). The treatment estimates from this model will represent an average percent change from baseline of spot urine oxalate:creatinine ratio across Month 3 through Month 6 at which the treatment effect is expected to have reached steady state. Furthermore, given the variability of spot oxalate:creatinine ratio, averaging the values across these visits will yield stable treatment estimates. Sensitivity analyses will be conducted to assess the robustness of the estimates and will be detailed in the SAP. In addition, descriptive statistics scheduled visit will be presented and by-patient listings and figures will be generated displaying all assessments (scheduled and unscheduled).

Secondary efficacy and exploratory endpoints which are continuous will be summarized descriptively in the same manner as described above. For binary endpoints, the number and percentages of patients in each category will be displayed at each visit.

#### **7.2.6. Pharmacodynamic Analysis**

Urinary oxalate and glycolate excretion, urinary oxalate:creatinine ratio and plasma levels of oxalate and glycolate will be summarized over time for all patients in the Efficacy Analysis Set.

### **7.2.7. Pharmacokinetic Analysis**

Pharmacokinetic analyses will be conducted using noncompartmental methods.

Pharmacokinetic parameters include, but will not be limited to:  $C_{max}$ ,  $t_{max}$ ,  $t_{\frac{1}{2}\beta}$ , AUC, CL/F, and V/F. Other parameters may be calculated, if deemed necessary.

### **7.2.8. Safety Analyses**

The main parameter is the frequency of treatment-emergent AEs (hereafter referred to simply as AEs). Safety parameters also include vital signs, ECGs, clinical laboratory assessments and physical exams. Extent of exposure will be summarized overall.

Prior and concomitant medications will be classified according to the World Health Organization (WHO) Drug Dictionary. Results will be tabulated by Anatomical Therapeutic Chemical (ATC) Classification System and Preferred Term (PT).

AEs will be classified according to the Medical Dictionary for Regulatory Activities (MedDRA) overall. AEs, SAEs, related AEs, and AEs leading to discontinuation will be summarized by System Organ Class (SOC) and PT for each treatment arm. By-patient listings will be provided for deaths, SAEs, and events leading to discontinuation of treatment.

Descriptive statistics will be provided for clinical laboratory data, ECG, and vital signs data. Laboratory shift tables from baseline to worst values will be presented.

Other safety summaries will be presented as appropriate. Further details will be specified in the SAP.

### **7.2.9. Immunogenicity Analyses**

Antidrug antibody results will be summarized descriptively by patient and overall.

### **7.2.10. Interim Analysis**

There may be interim analyses performed to support regulatory and/or publications requests.

### **7.2.11. Optional Additional Research**

Optional additional research may be conducted in the future on the biological samples and/or data collected during the study in accordance with the strict terms of the informed consent form (see Section 4.3.2).

## **8. STUDY ADMINISTRATION**

### **8.1. Ethical and Regulatory Considerations**

This study will be conducted in accordance with the protocol, all applicable regulatory requirements, and the current guidelines of Good Clinical Practice (GCP). Compliance with GCP provides public assurance that the rights, safety, and well-being of study patients are protected consistent with the principles that have their origin in the Declaration of Helsinki.

### **8.1.1. Informed Consent**

The Investigator will ensure that the patient or legal guardian is given full and adequate oral and written information about the nature, purpose, possible risk and benefit of the study. The patient or their legal guardian must also be notified that they are free to discontinue from the study at any time. The patient or legal guardian should be given the opportunity to ask questions and allowed time to consider the information provided. Legal guardian(s) must provide informed consent and the patient should provide assent per local regulations and institutional standards.

The patient's or legal guardian's signed and dated informed consent (or assent, if applicable) must be obtained before conducting any study tests or procedures that are not part of routine care.

When a patient under the age of legal consent who has been enrolled in the study reaches the legal age of consent, the Investigator must obtain the patient's informed consent or assent, as applicable, prior to performing any further research interventions and/or procedures involving that patient per local regulations and institutional standards.

The Investigator must maintain the original, signed ICF (assent form, if applicable). A copy of the signed ICF (assent form, if applicable) must be given to the patient or legal guardian.

The Investigator will inform the patient/legal guardian if new information becomes available that may be relevant to the patient's/legal guardian's willingness to continue participation in the study. Communication of this information should be documented.

### **8.1.2. Ethical Review**

The study protocol, including the ICF (assent form, if applicable), must be approved or given a favorable opinion in writing by an IRB or IEC, as appropriate. The Investigator must submit written approval before he or she can enroll any patient into the study.

The Investigator is responsible for informing the IRB or IEC of any amendment to the protocol in accordance with local requirements. In addition, the IRB or IEC must approve all patient materials for the study (except those that support the need to remove an apparent immediate hazard to the patient). The protocol must be reapproved by the IRB or IEC upon receipt of amendments and annually, as local regulations require.

Initial IRB or IEC approval of the protocol, and all materials approved by the IRB or IEC for this study including the legal guardian consent form and patient assent form, as applicable per institutional standards and recruitment materials must be maintained by the Investigator and made available for inspection.

The Investigator will submit reports of SAEs as outlined in Section [6.5.6](#). In addition, the Investigator agrees to submit progress reports to the IRB or IEC per their local reporting requirements, or at least annually and at the conclusion of the study. The reports will be made available to the Sponsor or designee.

Any communications from regulatory agencies, IRBs, or IECs in regard to inspections, other studies that impact this protocol or the qualifications of study personnel should be promptly reported to the Sponsor or its designee.

The Investigator is also responsible for providing the IRB or IEC with reports of any reportable serious adverse drug reactions from any other study conducted with the study drug. The Sponsor or designee will provide this information to the Investigator.

Major changes in this research activity, except those to remove an apparent immediate hazard to the patient, must be reviewed and approved by the Sponsor and the IRB or IEC that approved the study. Amendments to the protocol must be submitted in writing to the Investigator's IRB or IEC and the Regulatory Authority for approval before patients are enrolled under the amended protocol, and legal guardians must be re-consented to the most current version of the ICF (and patient assent form, as applicable).

### **8.1.3. Serious Breach of Protocol**

Investigators must notify the Medical Monitor within 24 hours of becoming aware of a potential serious breach of the protocol. A serious breach is a breach that is likely to affect to a significant degree the safety and rights of a study participant or the reliability and robustness of the data generated in the clinical trial.

### **8.1.4. Study Documentation, Confidentiality, and Records Retention**

All documentation relating to the study should be retained for 2 years after the last approval in an ICH territory or as locally required, whichever is longer. If it becomes necessary for the Sponsor, the Sponsor's designee, applicable IRB/IEC, or applicable regulatory authorities to review or audit any documentation relating to the study, the Investigator must permit direct access to all source documents/data. Records will not be destroyed without informing the Sponsor in writing and giving the Sponsor the opportunity to store the records for a longer period of time at the Sponsor's expense.

The Investigator must ensure that the patients' confidentiality will be maintained. On the eCRFs or other documents submitted to the Sponsor or designees, patients should not be identified by their names, but by the assigned patient number or code. If patient names are included on copies of documents submitted to the Sponsor or designees, the names will be obliterated, and the assigned patient number added to the document. Documents not for submission to the Sponsor (eg, signed ICFs) should be maintained by the Investigator in strict confidence.

The Investigator must treat all of the information related to the study and the compiled data as confidential, whose use is for the purpose of conducting the study. The Sponsor must approve any transfer of information not directly involved in the study.

To comply with local and/or regional regulations, this clinical study may be registered, and study results may be posted on public registries, such as ClinicalTrials.gov.

### **8.1.5. End of Study**

The end of study is defined as the last patient last visit.

### **8.1.6. Termination of the Clinical Study or Site Closure**

The Sponsor, or designee, reserves the right to terminate the study or a clinical study site at any time. Conditions that may warrant this action may include, but are not limited to:

- The discovery of an unexpected, serious, or unacceptable risk to patients participating in the study
- Failure of the Investigator to comply with the protocol, the requirements of the IRB/IEC or local health authorities, the sponsor's procedures, or GCP guidelines
- Inadequate recruitment of participants by the Investigator
- The decision on the part of the Sponsor to suspend or discontinue treatment with the study drug

Should the study be terminated, and/or the site closed for whatever reason, all documentation and study drug pertaining to the study must be returned to the Sponsor or its representative, and the Investigators, IRB/IEC and Regulatory Authorities will be promptly informed of the termination and the reason for the decision. The Investigator should promptly inform the patients and assure appropriate therapy and follow-up.

## **8.2. Data Quality Control and Quality Assurance**

### **8.2.1. Data Handling**

Study data must be recorded on CRFs (paper and/or electronic) provided by the Sponsor or designee on behalf of the Sponsor. Case report forms must be completed only by persons designated by the Investigator. If eCRFs are used, study data must be entered by trained site personnel with access to a valid and secure eCRF system. All data entered into the eCRF must also be available in the source documents. Corrections on paper CRFs must be made so as to not obliterate the original data and must be initialed and dated by the person who made the correction.

### **8.2.2. Study Monitoring**

The Monitor, as a representative of the Sponsor, has an obligation to closely follow the study conduct at the site. The Monitor will visit the Investigator and clinical study center periodically and will maintain frequent telephone and written contact. The Monitor will maintain current personal knowledge of the study through observation, review of study records and source documentation, and discussion of the conduct of the study with the Investigator and staff.

The Monitor will review source documents, systems and CRFs to ensure overall quality and completeness of the data and to confirm study procedures are complied with the requirements in the study protocol accurately. The Sponsor, or its designee, will be allowed to conduct site visits to the investigation facilities for the purpose of monitoring any aspect of the study. The Investigator agrees to allow the Monitor to inspect the drug storage area, study drug stocks, drug accountability records, patient charts and study source documents, site standard operating procedures and training records, and other records relative to study conduct.

### **8.2.3. Audits and Inspections**

Periodically, the Sponsor or its authorized representatives audit clinical investigative sites as an independent review of core trial processes and documents to determine whether these activities were conducted, and data were recorded, analyzed, and accurately reported according to the

protocol, GCP guidelines of the ICH, and any applicable regulatory requirements. A regulatory authority, an IEC or an IRB may visit the site to perform audits or inspections, including source data verification. The Investigator should contact the Sponsor and designee immediately if contacted by a regulatory agency, an IEC or an IRB about an inspection.

### **8.3. Publication Policy**

It is intended that after completion of the study, the data are to be submitted for publication in a scientific journal and/or for reporting at a scientific meeting. A separate publication by Institution or Investigator may not be submitted for publication until after this primary manuscript is published or following the period of 12 months after completion of the study at all centers. A copy of any proposed publication (eg, manuscript, abstracts, oral/slide presentations, book chapters) based on this study, must be provided and confirmed received at the Sponsor at least 30 days before its submission. The Clinical Trial Agreement among the institution, Investigator, and Alnylam will detail the procedures for Alnylam's review of publications.

Authorship of any publications resulting from this study will be determined on the basis of the Uniform Requirement for Manuscripts Submitted to Biomedical Journals (International Committee of Medical Journal Editors).

## 10. APPENDICES

### 10.1. Formulae for Estimated Glomerular Filtration Rate Calculation

Estimated glomerular filtration rate (eGFR; in mL/min/1.73m^2) will be calculated from serum creatinine (SCr) based on the Schwartz Bedside Formula for patients  $\geq$ 12 months of age at the time of assessment.

#### Schwartz Bedside Formula [Schwartz 2009]

- Conventional units
  - $eGFR \text{ (mL/min/1.73 m}^2\text{)} = (0.413 \times \text{height [cm]})/\text{SCr (mg/dL)}$
- SI units
  - $eGFR \text{ (mL/min/1.73 m}^2\text{)} = (36.2 \times \text{height [cm]})/\text{SCr (\mu mol/L)}$

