#### **Laboratory Assessments**

1. Has any of the following laboratory parameter assessments:
  - a. Alanine aminotransferase (ALT) or aspartate aminotransferase (AST)  $>2\times$  ULN for age during screening
  - b. Total bilirubin  $>1.5\times$  ULN during screening. Patients with elevated total bilirubin that is secondary to documented Gilbert's syndrome are eligible if the total bilirubin is  $<2\times$  ULN
2. Has known active human immunodeficiency virus (HIV) infection, or evidence of current or chronic hepatitis C virus (HCV) or hepatitis B virus (HBV) infection.
3. If  $\geq 12$  months old at screening, has an estimated glomerular filtration (GFR) of  $\leq 45$  mL/min/1.73m^2 (calculation will be based on the Schwartz Bedside Formula) at

screening; if <12 months old at screening, has serum creatinine value per the central laboratory above the ULN for age at screening.

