### **6.3.2. Estimated Glomerular Filtration Rate**

Blood samples for the assessment of eGFR will be obtained at the time points specified in the Schedules of Assessment (see [Table 1](#), [Table 2](#), [Table 3](#), and [Table 4](#)). eGFR (mL/min/1.73 m^2) will be calculated in patients  $\geq$ 12 months of age at the time of the assessment to evaluate renal function during the study. The calculation will be based on the Schwartz Bedside Formula (Appendix [10.1](#)).[Levey 2009; Schwartz 2009]

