3.2. Secondary Endpoints

Extension Phase

- Percent change in urinary oxalate excretion from baseline
- Percentage of time that spot urinary UOx:Cr ratio is at or below the near-normalization threshold ($\leq 1.5 \times \text{ULN}$ for age)

Duration of Study

- Absolute change in urinary oxalate excretion from baseline
- Change (percent and absolute) in plasma oxalate concentration from baseline
- Proportion of patients with urinary oxalate excretion \leq the upper limit of normal (ULN) for age and $\leq 1.5 \times \text{ULN}$ for age
- Plasma PK parameters of lumasiran
- Change in estimated glomerular filtration rate (eGFR) from baseline

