where cumulative months in near-normalization will be defined as the summation across all intervals that met the near-normal threshold and cumulative months of valid assessments will be defined as the summation across all valid post-baseline collections.

Given that the sample collection varies during the study, the calculation of percentage of time will include the following considerations:

- Time will include all follow-up assessments until study end or premature treatment discontinuation, whichever occurs first.
- A linear interpolation method will be used to determine the bookend dates at which the patient crossed into the normal threshold and crossed out of the normal threshold

Descriptive statistics of percentage of time at or below the threshold (among the subset of patients who had at least one post-baseline value that met threshold) will be presented. In addition, the number of patients and associated percentage of patients in each category (e.g. <25%, ≥25% to <50%, ≥50% to <75%, ≥75% of time at or below the threshold) will also be presented.

Descriptive statistics of eGFR at and after 6 months of lumasiran will be presented using the Efficacy Analysis Set and Safety Analysis Set. Shift tables of eGFR categories from baseline to post-baseline visits and an overall worst post-baseline will also be generated

To demonstrate durability of the treatment effect of lumasiran, additional secondary endpoints may be assessed.

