7.7.3. Clinical Laboratory Data

Clinical laboratory parameters will be expressed in Standard International (SI) units. Laboratory data collected and recorded as below the lower limit of quantitation (LLOQ) will be set to the LLOQ for calculation of summary statistics. Key laboratory parameters will be graded according to NCI CTCAE v5.0.

Clinical laboratory data by visit in summary tables will use data from central laboratory.

eDISH plots and the summary tables and listings for abnormality for clinical laboratory data will be analyzed in two ways; one using only central laboratory data and one using both central and local laboratory data by the following rules;

- Central laboratory data at both scheduled and unscheduled visits will be used.
- If central laboratory data at a visit is missing, local laboratory data will be used.
- If a patient has both local and central laboratory data at the same visit, the central data will be used.

Shift tables will be generated to summarize shifts from baseline category to the worst post-baseline category with directionality specified (e.g. hyper and hypo).

Clinical laboratory tests with normal ranges will be classified as Low, Normal, and High. For these tests, abnormal values will be flagged in the listings with H when the value is higher than the upper limit of the reference ranges and with L when the value is lower than the lower limit of the reference ranges.

For hematology and chemistry labs, summary tables of potentially clinically significant abnormalities may also be provided.

- All laboratory data will be presented in data listings. The listing of the clinical laboratory data will display both local and central laboratory data. Out of range laboratory results will be identified in listings.

LFTs: A listing will be generated for all patients with abnormal liver function tests as defined by alanine aminotransferase (ALT)>3xULN, aspartate aminotransferase (AST)>3xULN or total bilirubin >2x ULN at any visit.

A tabular summary for LFTs will be generated to summarize the number and associated percentage of patients in each of the categories at any post-baseline visit:

- ALT: Within normal limit (WNL), $1 < \text{ALT} \leq 3$, $3 < \text{ALT} \leq 5$, $5 < \text{ALT} \leq 10$, $10 < \text{ALT} \leq 20$, $\text{ALT} > 20 \times \text{ULN}$
- AST: WNL, $1 < \text{AST} \leq 3$, $3 < \text{AST} \leq 5$, $5 < \text{AST} \leq 10$, $10 < \text{AST} \leq 20$, $\text{AST} > 20 \times \text{ULN}$

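### Protocol Appendix 10.1 prints the bedside eGFR formula with constants 0.413 (mg/dL) and 36.2 (µmol/L), which do not convert into each other; 0.413 corresponds to about 36.5

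*Protocol*

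**What the plan says.** Appendix 10.1 of the protocol presents a single equation, the bedside Schwartz formula, for patients aged at least 12 months at the assessment, and prints it twice:

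- Conventional units, serum creatinine in mg/dL: "0.413 \times \text{height [cm]})/\text{SCr (mg/dL".
- SI units, serum creatinine in µmol/L: "36.2 \times \text{height [cm".

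The equation is used in four places:

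- **Eligibility.** Protocol 4.2, exclusion criterion 3, rejects a child of 12 months or more with an eGFR of 45 mL/min/1.73 m² or below, and says the "calculation will be based on the Schwartz Bedside Formula".
- **On-study renal function.** Protocol 6.3.2 points to Appendix 10.1: "The calculation will be based on the Schwartz Bedside Formula".
- **Secondary endpoint.** SAP 3.2 lists "Change in estimated glomerular filtration rate (eGFR) from baseline".
- **Category tables.** SAP 7.3 plans "Shift tables of eGFR categories from baseline to post-baseline visits".

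The SAP prints no eGFR equation. On units, SAP 7.7.3 states: "Clinical laboratory parameters will be expressed in Standard International (SI) units". The same section takes by-visit laboratory summaries from the central laboratory.

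**The concern.** If both lines express the same formula, the same blood sample must give the same eGFR whichever unit the laboratory reports. That requires the SI constant to equal the conventional constant multiplied by the number of µmol/L in 1 mg/dL of creatinine. The printed pair does not appear to satisfy this.

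A child near the cut-off could then be eligible by one line and excluded by the other. An analyst working in SI units could also fail to reproduce eGFR values calculated in conventional units. If the two lines were mixed between laboratories or visits, a small artificial change would enter a secondary endpoint that is itself a change from baseline.

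**Working it through.** **Inputs.** From Appendix 10.1: k = 0.413 (mg/dL) and k(SI) = 36.2 (µmol/L). From exclusion criterion 3: the cut-off of 45. Assumed, because the documents do not give it: a creatinine factor f of 88.4 µmol/L per mg/dL (10,000/113.12 g/mol = 88.40), with a range of 88.0 to 88.5.

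**Step 1. Try to reproduce 36.2.** k(SI) = k × f.

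| f | 0.413 × f | 36.2 / f | 36.2 / (0.413 × f) | SI line lower by |
|---|---|---|---|---|
| 88.0 | 36.34 | 0.4114 | 0.9960 | 0.40% |
| 88.4 | 36.51 | 0.4095 | 0.9915 | 0.85% |
| 88.5 | 36.55 | 0.4090 | 0.9904 | 0.96% |

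The printed 36.2 is not reproduced at any factor in the range. Both constants would hold only with f = 36.2/0.413 = 87.65, which implies a creatinine molar mass of 10,000/87.65 = 114.09 g/mol instead of 113.12.

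**Step 2. Is it rounding?** Take the smallest value that rounds to 0.413 and the lowest factor in the range: 0.4125 × 88.0 = 36.30. A printed 36.2 can stand for at most 36.25, so rounding at the printed precision does not close the gap. At f = 88.4, values that round to 0.413 give 36.47 to 36.55. The one variant tried that lands on 36.2 starts from a constant cut to two decimals: 0.41 × 88.4 = 36.24.

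**Step 3. Effect at the cut-off.** A child at exactly 45.0 by the conventional line has 45 × 0.9915 = 44.6 by the SI line. The two lines disagree on eligibility for conventional values above 45.00 and up to 45/0.9915 = 45.38 (45.18 at f = 88.0, 45.44 at f = 88.5).

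At an illustrative height of 90 cm and f = 88.4, the band in creatinine is:

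- lower end: 36.2 × 90/45 = 72.4 µmol/L, and 72.4/88.4 = 0.819 mg/dL
- upper end: 0.413 × 90/45 = 0.826 mg/dL, and 36.51 × 90/45 = 73.0 µmol/L

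Its width is 0.826 − 0.819 = 0.007 mg/dL. If creatinine is reported in steps of 0.01 mg/dL (an assumption), one step already moves eGFR by more than the discrepancy: 0.413 × 90/0.82 − 0.413 × 90/0.83 = 45.33 − 44.78 = 0.55.

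Example: for a child of 90 cm with creatinine 0.82 mg/dL (72.5 µmol/L), the conventional line gives 0.413 × 90/0.82 = 45.33 and the SI line gives 36.2 × 90/72.5 = 44.94. The first is eligible and the second is excluded.

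**Step 4. Effect on the endpoint.** With one line used throughout, the ratio 0.9915 cancels from percent change and rescales absolute change: a change of 10 becomes 10 × 0.9915 = 9.92. The documents do not give the eGFR category boundaries for the shift tables, so movement between categories cannot be sized.

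**The case against.** There are three fair objections.

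First, this may only be one constant carried at two precisions, since 0.41 × 88.4 = 36.24. That is a plausible origin, although the documents cannot confirm it. It does not reconcile the appendix, because 0.413 is what is printed there.

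Second, the choice of line is less open than it looks. Each line is labelled by its creatinine unit. Protocol 6.5.5 and Table 10 make the central laboratory the default and prefer its results when local and central values differ. SAP 7.7.3 sets SI units and central data for by-visit summaries. This stands for the by-visit analysis, where the SI line is the natural reading. It does not settle screening, for which no document names a line or a unit. Local laboratories may also be used when blood volume is limiting, and SAP 7.7.3 admits local values to one version of the abnormality summaries when central values are missing. Mixing is therefore possible, but nothing in the documents shows that it happened.

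Third, the consequence is minor: under 1%, a descriptive secondary endpoint with no test of eGFR, and an eligibility band narrower than one assumed reporting step. This stands in full and sets the weight of the point.

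**Conclusion.** The inconsistency is real, and it sits in current protocol text that the trial relies on. As printed, the two lines are not unit conversions of each other. The SI line gives an eGFR about 0.85% lower at the assumed factor of 88.4, and 0.40% to 0.96% lower over 88.0 to 88.5. The conversion factor is the only outside input on which the inconsistency rests, and the conclusion holds across that range.

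The practical weight is low. Children under 12 months have no eGFR calculated and are unaffected, as is the primary endpoint. Few or none of the 20 planned patients are likely to fall in the eligibility band. The documents do not show which constant is the intended one or which the central laboratory used. This is a minor correction.

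**What to change.** Check both constants against the source cited in Appendix 10.1 and print a pair that agrees to the same precision. If 0.413 is confirmed, the matching SI value at a factor of 88.4 is 36.5. State in Appendix 10.1 and in the SAP that one version is used for screening, baseline and all later visits, and give the conversion factor applied when a laboratory reports in the other unit. Then check the eGFR derivation program against that version.

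The cost is one constant and one sentence in the appendix, one sentence in the SAP, and a program check.
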